ORI IRB# 00000278

Protocol Version 11.6.2018

Official Title: Talk STEM Familia: A Language Acquisition Smart Speaker-Based App to Improve English Language Acquisition And Family Engagement and Promote Long-Term Educational and Health Outcomes Among First- and Second-Generation Latino Families

Principal Investigators: [name], [name].

Influents Innovations

Award No. R43MD013619 - 01

Protocol Version Date: 11.6.2018

Study Protocol

We conducted a 6-week intervention among 50 dyads (4th/ 5th grade Latino English learners and their parent) to assess feasibility of *TSF* in terms of its usefulness, ease-of-use, cultural appropriateness, and potential for efficacy. The test used a within-subjects pre-post design to detect changes in student and parent word knowledge, self-efficacy, and behavioral intention. We also collected a post-test evaluation of consumer satisfaction and student and parent recommendations for program modifications.

Statistical Analysis Plan

The evaluation had three main goals: (a) determine whether statistically significant effects were found between T1 (pretest) and T2 (posttest) on the outcome measures; (b) determine the program effect sizes; and (c) determine the parent's and student's reaction to the program and amount of program use. An intent-to-treat analysis using one fully-imputed dataset and paired t-tests were used to determine whether or not there were significant increases in the outcome measures from pretest to posttest. The point-biserial r is provided as a measure of effect sizes with the convention .14 small, .36 medium, and .51 large (Rosenthal & Rosnow, 2008). Examination of descriptive statistics for the user satisfaction items informed on parent's and student's reaction to the program.

Power Analysis

Based on the pre-post within-subject design with 50 student-parent dyads, accounting for 10% attrition, and a two-tailed alpha set to .05, the study would have sufficient statistical power ($> .80$) to detect a medium or larger effect size (Cohen's $d = .41$) for change in the proposed outcomes. We believe that these differences are not so small as to be meaningless to participants, but not so large as to represent unrealistic expectations of changes brought about by the intervention. For ancillary analyses involving correlations the study is powered to detect medium or larger effects ($r = .38$).

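### Does testing four to six pre-post outcomes at .05, with no primary outcome and no adjustment, call for a multiplicity rule?

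*Combined protocol and SAP*

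**What the plan says.** The Study Protocol section describes a six-week, single-group, pre-post study of 50 dyads. It assesses feasibility in terms of "usefulness, ease-of-use, cultural appropriateness, and potential for efficacy", and its design is meant to "detect changes in student and parent word knowledge, self-efficacy, and behavioral intention".

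The Statistical Analysis Plan lists three main goals without ranking them. Goal (a) is to "determine whether statistically significant effects were found between T1 (pretest) and T2 (posttest) on the outcome measures", goal (b) is to "determine the program effect sizes", and goal (c) concerns participants' reaction to the program and how much they used it. Paired t-tests are to "determine whether or not there were significant increases in the outcome measures from pretest to posttest".

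The only significance level appears in the Power Analysis: "accounting for 10% attrition, and a two-tailed alpha set to .05". There the study is said to have power above .80 at d = .41 "for change in the proposed outcomes". The outcomes are not listed or counted. No primary outcome, adjustment or exploratory label is given for the pre-post tests.

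**The concern.** Goal (a) is put in terms of statistical significance over several outcomes, and the plan has no rule for reading a mixed set of p-values. If each test is run at .05, the chance that at least one comes out significant by luck is well above the chance for a single test. One or two nominal hits could then be reported as significant effects with no mention of how many tests were run.

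The plan does have a lower-tier label, ancillary, but applies it only to correlations. A reader could infer that the pre-post tests are meant as firm inference. At stake is how the results are interpreted and reported. The data collected, the design and the participants are not affected.

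**Working it through.** **Inputs.** From the documents: 50 dyads, 10% attrition (50 × .9 = 45), two-tailed alpha .05, d = .41. Assumed: the number of tests k and the correlation ρ between the outcomes' changes. k is 6 if student and parent apply to all three constructs, and 4 if they apply to word knowledge only. It would be higher if a construct has several scales. The documents give no ρ, so 0, .5 and .8 are shown. That each test uses .05 unadjusted is inferred, because no adjustment is mentioned.

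**1. The plan's own power figure.** Normal approximation: power = Φ(d√n − 1.96).
- n = 45: Φ(.41 × 6.708 − 1.96) = Φ(.790) = .785.
- n = 50: Φ(.41 × 7.071 − 1.96) = Φ(.939) = .826.
- Exact noncentral t: .767 at n = 45 and .811 at n = 50.

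The stated figure is therefore met with all 50 dyads and narrowly missed with 45. Either way it is the power of one test at an unadjusted .05.

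**2. Chance of at least one nominal hit if nothing changes.** With independent outcomes:
- Either direction: 1 − .95^6 = .265; 1 − .95^4 = .185.
- Increases only: 1 − .975^6 = .141; 1 − .975^4 = .096.

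With common correlation ρ and c = 1.96, the increases-only chance is 1 − ∫ [Φ((c − √ρ·u)/√(1−ρ))]^k φ(u) du. The two-sided version subtracts Φ((−c − √ρ·u)/√(1−ρ)) inside the bracket.

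| k | direction | ρ = 0 | ρ = .5 | ρ = .8 |
|---|---|---|---|---|
| 6 | either | 26.5% | 20.7% | 13.9% |
| 4 | either | 18.5% | 15.6% | 11.4% |
| 6 | increases | 14.1% | 10.4% | 6.9% |
| 4 | increases | 9.6% | 7.8% | 5.7% |

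The single-test rates are 5% and 2.5%. Simulated paired t-tests at n = 45 and n = 50 agree to within about one percentage point. The expected number of false increases is at most 6 × .025 = .15, whatever the correlation.

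**3. Which row applies.** The tests are described as looking for increases, so the lower two rows fit best, although the wording of goal (a) also allows the upper two. Full independence is doubtful for three measures on the same person. At ρ from .5 to .8 the chance of a false increase is 5.7 to 10.4%.

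**4. Price of a binding adjustment.** Power per outcome at d = .41, exact t, Bonferroni:

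| level | n = 45 | n = 50 |
|---|---|---|
| .05 | .767 | .811 |
| .05/4 | .562 | .621 |
| .05/6 | .501 | .563 |

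Holm over six tests, simulated at ρ = .5 with 1, 3 or 6 outcomes truly at d = .41, gives .501, .528 and .609 at n = 45, and .564, .592 and .674 at n = 50. Under Bonferroni over six tests, a real effect of the planned size would be missed about half the time with 45 dyads (1 − .501 = .499).

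**The case for a change.** The strongest case for a change is that asking whether effects are significant is an inferential question, and describing the study as feasibility work does not tell a reader how to take one significant result out of six. The remedy could also be light: list and count the outcomes, label the tests exploratory, add confidence intervals, and show Holm-adjusted p-values beside the unadjusted ones without making them binding. None of that needs new data, and intervals would help. At n = 45 an observed d of .41 has a 95% interval of about .10 to .71.

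Part of this stands. The outcomes should be listed and counted, and a report would be better with intervals. But listing, labelling and a non-binding column write down detail and change no test result. The one element with force would be a ban on unqualified significance statements from unadjusted p-values. That comes close to binding adjustment and carries the power cost shown above. Statisticians can reasonably differ on whether to pay it in a 50-dyad feasibility study.

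Adjustment would also do little against a larger threat to an efficacy reading. With no control group, retesting and ordinary learning over six weeks could raise scores without any program effect, and Holm does nothing about that. Nothing in the plan suggests selective reporting, since the goals and tests refer to the outcome measures as a whole.

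**Conclusion.** No change to the plan is needed. The plan does leave out the number of tests and how a mixed set of results should be read. The inflated error rate, however, belongs to a rule that any one hit counts as success, and the plan contains no such rule and claims no family-wise control. Potential for efficacy is one of four feasibility aspects, and effect sizes and user reaction stand beside significance as main goals.

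The size is modest: about 6 to 10% for at least one false increase at assumed correlations of .5 to .8, and 14% for six independent outcomes. Keeping unadjusted tests in order to retain power near .77 to .81, rather than about .50 to .67 under six-test Bonferroni or Holm, is a fair trade-off at this stage. The missing list is filled sensibly by reporting all outcomes together with their effect sizes.

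These figures rest on four or six tests, on assumed correlations, and on reading the plan's silence as no adjustment. More scales per construct would raise them, and correlations above .8 would lower them. The conclusion would not extend to a report that claimed efficacy from a single significant outcome, but that would be a fault in the report and not in this plan.

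### Paired t-tests on a single imputed dataset understate the standard error: a nominal 5% test runs at about 7% if the planned 10% of posttests are regression-imputed, and at less if fewer are.

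*Combined protocol and SAP*

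**What the plan says.** The Statistical Analysis Plan gives three goals, the first being to establish whether outcomes changed significantly between T1 and T2. The method for that goal is: "An intent-to-treat analysis using one fully-imputed dataset and paired t-tests were used", the purpose being "to determine whether or not there were significant increases in the outcome measures from pretest to posttest". No imputation model is named. There is no pooling rule, variance adjustment, count of imputed values or sensitivity analysis.

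The Power Analysis sets the standard the tests should meet and the only missing-data figure available: "accounting for 10% attrition, and a two-tailed alpha set to .05". The sample is 50 student-parent dyads in a within-subject design with no control arm.

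**The concern.** A paired t-test on a completed file of 50 rows uses SD/√50 and 49 degrees of freedom, whichever rows were measured. A posttest predicted by regression from the other participants adds no independent information about change. Counting it as an observation therefore makes the reported standard error too small. Adding one random draw to each prediction does not cure this, because the uncertainty about the filled-in values still does not enter the standard error.

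Goal (a) rests on these p-values. The outcomes tested are student and parent word knowledge, self-efficacy and behavioral intention, and each one with regression-imputed posttests would be tested at more than its stated .05. Under no true change and data missing completely at random, the excess falls about equally in both directions, so false findings of an increase also become more frequent.

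**Working it through.** **Inputs from the document.** 50 dyads; 10% attrition, so 0.10 × 50 = 5 missing posttests; two-tailed alpha .05; one completed dataset; paired t-test; d = .41 with power above .80.

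**Assumptions, not in the document.** Bivariate normal scores with equal variances, no true change, posttests missing completely at random, regression of posttest on pretest as the imputation model, and pre-post correlation ρ from .3 to .9.

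**Step 1: the plan's own power figure.** With 50 analysed, the noncentrality is .41 × √50 = 2.90 and the noncentral t gives power .811, so the stated figure reproduces. With 45 analysed, .41 × √45 = 2.75 and power is .767 (.785 by the normal approximation); 80% power would need d of about .43. This is a side observation and does not affect the point below.

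**Step 2: standard error, analytic check.** Let n = 50, m = number imputed, k = n − m, with unit variances. For deterministic regression imputation, approximately:

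- True variance of the mean change: (1 − ρ²)/k + (1 − ρ)²/n
- Variance the t-test reports: [k · 2(1 − ρ) + m(1 − ρ)²]/n²

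At m = 5 and ρ = .5:

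- True: .75/45 + .25/50 = .01667 + .00500 = .02167
- Reported: (45 × 1 + 5 × .25)/2500 = 46.25/2500 = .01850
- Ratio of standard errors: √(.02167/.01850) = 1.082

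The critical value 2.010 (49 df) therefore acts as 2.010/1.082 = 1.857, and the two-sided rejection rate is 6.9%. For 5 imputed:

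| ρ | True variance | Reported variance | SE ratio | Type I error |
|---|---|---|---|---|
| .3 | .03002 | .02618 | 1.071 | 6.7% |
| .5 | .02167 | .01850 | 1.082 | 6.9% |
| .7 | .01313 | .01098 | 1.094 | 7.2% |
| .9 | .00442 | .00362 | 1.105 | 7.5% |

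**Step 3: simulation.** Runs of 60,000 replicates per setting covered deterministic regression and single stochastic draws, with ρ from .3 to .9:

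| Posttests imputed | Type I error |
|---|---|
| 0 | 4.9-5.1% |
| 1 | 5.2-5.6% |
| 2 | 5.4-6.0% |
| 5 | 6.7-7.7% |

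An independent simulation (100,000 per setting, 5 imputed) gave 6.6-7.4% for ρ of .3 to .7, 7.5-7.6% at ρ = .9 and 6.2-6.4% at ρ = 0. Missingness depending on the pretest gave 6.9-7.6%. A further run gave 6.6-7.7%. At 5 imputed, the rejections split into 3.3-3.9% upward and 3.3-3.8% downward, against 2.5% each way.

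If more posttests are missing than planned, the rate rises. With 10 imputed and ρ from .3 to .9 it is 8.5-11.3%.

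**Step 4: other methods with 5 missing.**

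| Method | Type I error |
|---|---|
| Posttest-mean imputation | 5.9-6.4% |
| Pretest carried forward | 4.9-5.1% |
| Completers only | 4.9-5.1% |
| Multiple imputation, Rubin's rules, small-sample df | 4.7-5.0% |

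**Step 5: which reported results could change.** Multiply the 44-df critical value, 2.015, by the SE ratio and convert back to a p-value on 49 df. A ratio of 1.07 gives t = 2.156 and p = .036; 1.10 gives t = 2.217 and p = .031; 1.11 gives t = 2.237 and p = .030. A reported p must fall below about .030 to .036 for the corrected p to be below .05.

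**Step 6: effect size, goal (b).** At d = .41 with 5 imputed, mean r moves from .38 to .39 under deterministic regression and stays at .38 under a stochastic draw.

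**The case against.** The strongest reply is that the 7% depends on facts the document does not supply. It requires a regression-type imputation and about five imputed values per outcome, whereas the 10% is an allowance in a power calculation and not a count of what was imputed. The study is reported in the past tense, so the true number is fixed but unseen. With one or two values the inflation is slight, and with the pretest carried forward there is none. This stands as a limit on the size in this study. It does not rescue the method: the stated analysis has no means of reflecting imputation uncertainty, and leaving out the model and the counts is what prevents a reader from checking.

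A second reply is that this is a feasibility study, only borderline p-values are exposed, and goals (b) and (c) are essentially unaffected. That is fair and keeps the consequence moderate. Goal (a) is nonetheless framed as significance testing at a declared alpha.

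A third is that informative dropout in an uncontrolled pre-post study may matter more than a standard error that is 7-11% too small, and multiple imputation under missing at random would not remove that bias. This also stands. It is a separate problem and calls for a separate sensitivity analysis.

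**Conclusion.** The concern holds. As written, the analysis treats imputed posttests as measured, and nothing elsewhere in the document corrects for it. With 5 of 50 posttests regression-imputed once, the nominal 5% test runs at about 7% (6.6-7.7% for correlations .3 to .9). With fewer imputed the excess shrinks, and with none it disappears. The mechanism is certain. The size in this study is conditional on the unstated imputation model, the unstated counts and the assumptions listed above. It should be fixed, with moderate consequence: p-values near .05 are unreliable, while clearly significant results and effect sizes are not materially affected.

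**What to change.** Replace the single completed dataset with multiple imputation (for example at least 20 imputations, with T1 scores in the model), and pool the mean change by Rubin's rules with small-sample degrees of freedom. Alternatively, fit a REML repeated-measures model with time as a fixed effect to all observed scores, stating the covariance structure and the degrees-of-freedom method.

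In either case, name the imputation model that was used and report the number of posttests imputed for each outcome. That disclosure comes first, because it shows which outcomes need re-analysis; those with no missing posttest are unchanged.

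Optionally, add a sensitivity run that assigns dropouts no change from T1. It addresses bias from informative dropout, not the standard error.

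The cost is a short re-analysis, since the tests have already been run, plus revised SAP wording. No new data are needed, and p-values for affected outcomes should become slightly larger.

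### Does the SAP need confidence intervals and a stated formula for r, given that goal (b) is served by a point r with size labels?

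*Combined protocol and SAP*

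**What the plan says.** The Statistical Analysis Plan section lists three main goals, the second being "b) determine the program effect sizes". For testing, "paired t-tests were used to determine whether or not there were significant increases in the outcome measures", in an intent-to-treat analysis of one fully imputed dataset. For effect size: "The point-biserial r is provided as a measure of effect sizes with the convention .14 small, .36 medium, and .51 large", with a literature reference attached.

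The Study Protocol section says that the design is meant to "detect changes in student and parent word knowledge, self-efficacy, and behavioral intention", so the effect sizes cover several outcomes in two kinds of participant.

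The Power Analysis gives its target as Cohen's d = .41, "for change in the proposed outcomes", and describes it as at least a medium effect. It does not name the SD that divides the change. No section mentions a confidence interval or a formula for r.

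**The concern.** The planned quantity for a main goal is a point value set beside three thresholds. With 45 to 50 pairs, the sampling error of r is wide compared with the gaps between .14, .36 and .51. The same true effect can therefore be called small in one study and large in the next. A reader given only r and its label would not see this.

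The missing formula adds to the worry. More than one conversion from d to r is in use, and the planned effect is medium under one and small under another. If the plan left that open, the label could depend on an unrecorded choice. At stake would be how far a reader could rely on the stated size of the program's effect when judging its potential.

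**Working it through.** **Inputs.** From the Power Analysis: 50 dyads; "accounting for 10% attrition", which leaves 50 × 0.90 = 45 if taken off the 50; "a two-tailed alpha set to .05"; d = .41; power above .80. From the Statistical Analysis Plan: paired t-tests and cut-offs .14, .36, .51. Assumed, because not stated: normal change scores, d = mean change / SD of change, r derived from the paired t, and cut-offs used as lower bounds of bands.

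**1. The plan's own figure.** The noncentrality of the paired t is d√n.
- n = 50: .41 × √50 = 2.899; exact two-sided power .811.
- n = 45: .41 × √45 = 2.750; exact two-sided power .767.

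The claim of more than .80 reproduces when all 50 are analysed, as in the imputed intent-to-treat set, though not with 45. It is consistent with d on the SD of change.

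**2. Which r the plan implies.**
- Paired-t form: r = d/√(d² + 1) = .41/√1.1681 = .379. The .36 cut-off corresponds to d = .36/√(1 − .36²) = .386, so d = .41 is medium.
- Two-group form: r = d/√(d² + 4) = .41/√4.1681 = .201. The .36 cut-off corresponds to d = 2 × .386 = .772, so d = .41 is small.

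Set against the SAP's cut-offs, only the first form agrees with the Power Analysis, which calls d = .41 at least medium. It is also the natural form beside a paired t-test.

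**3. How often the label is right under that form.** With r = t/√(t² + df), a cut-off c corresponds to t = c√(df/(1 − c²)). For n = 50 (df 49) the t cut-offs are .990, 2.701 and 4.150; for n = 45 (df 44) they are .938, 2.560 and 3.933. The noncentral t with the noncentralities from step 1 gives:

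| n | below small | small | medium | large | not medium |
|---|---|---|---|---|---|
| 50 | 2.8% | 39.1% | 45.3% | 12.8% | 54.7% |
| 45 | 3.5% | 38.6% | 43.6% | 14.2% | 56.4% |

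Part of this is a boundary effect: .379 lies only .019 above .36. It is not all boundary, because a true r at mid-band (.435) is labelled medium with probability only .51 (n = 50) or .48 (n = 45).

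**4. Interval at an observed d of .41** (inverting the noncentral t, then r = d/√(d² + 1)).
- n = 50: d from .119 to .697, r from .12 to .57.
- n = 45: d from .103 to .712, r from .10 to .58.

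**5. How much depends on the reading.** Chance of a wrong label at the planned effect, n = 45 to 50:
- two-group form: 19.9% to 21.6%;
- paired-t form, labelling by nearest benchmark: 47% to 49%;
- d on the raw-score SD with an assumed pre-post correlation of .3 to .8: about 34% to 56% with the paired-t r, about 8% to 26% with a group-type r.

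**6. What an interval would add.** Under the paired-t form, r and n already determine t. With n = 50 and an observed r of .383 (.3826 unrounded), t = .3826 × √(49/(1 − .3826²)) = 2.90, and the interval in step 4 follows. The interval displays the uncertainty; it leaves every entry in the step 3 table as it is.

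**The case for a change.** The best case for a change is that effect size is a named main goal, and that a point r with an adjective does not convey what 50 dyads can establish. An interval from below the small cut-off to above the large one is informative, and it costs a line of output per outcome. The planned effect's own label turns on the formula (.38 or .20), so one sentence would remove real doubt. The plan's past tense is no obstacle, because the report can still carry both.

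Much of this stands. The omissions are real, the arithmetic is right on its stated reading, and the imprecision is large even away from a cut-off.

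Three parts do not carry the case. First, a mislabelling rate cannot argue for intervals, since an interval does not lower it. Second, the formula is less open than it looks: the paired t-test, the reference to change in the outcomes and the description of d = .41 as medium all point the same way. The cited source may also fix it, which cannot be checked here. Third, the SAP offers r as one measure of effect size and nowhere says that the label is itself the answer to goal (b).

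The gain from intervals is also not entirely clean. In a single imputed dataset, filled-in values are treated as observed, so ordinary intervals would tend to be too narrow if data are missing.

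**Conclusion.** No change to the plan is called for. This is missing reporting detail that an analyst fills sensibly: r from the paired t, d on the SD of change, and intervals given alongside in the report. The documents contain no internal conflict on this point. Following them as written gives the same tests, p-values and conclusions about significance, and no decision depends on whether an effect is called small, medium or large. The study's stated purpose is feasibility and potential for efficacy.

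The imprecision itself should not be played down. On the paired-t reading, with normal change scores and cut-offs as lower bounds, a true effect of d = .41 misses its medium label in about 55% of studies, and the interval for r is about .12 to .57 at n = 50 or .10 to .58 at n = 45. The 55% is conditional: across the other readings in step 5 the figure runs from about 8% to 56%. The small sample drives this imprecision, and different wording in the SAP would not reduce it.

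### At 45 pairs (50 dyads less the plan's 10% attrition), a paired t-test has power of about .77 for d = .41, not the stated > .80: a modest shortfall that one sentence can fix.

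*Combined protocol and SAP*

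**What the plan says.** The Power Analysis section gives its basis as follows: "Based on the pre-post within-subject design with 50 student-parent dyads". The sentence goes on: "accounting for 10% attrition, and a two-tailed alpha set to .05, the study would have sufficient statistical power" (given as > .80) "to detect a medium or larger effect size (Cohen's $d = .41$) for change in the proposed outcomes". It then adds: "For ancillary analyses involving correlations the study is powered to detect medium or larger effects ($r = .38"), with no power or alpha attached to that sentence.

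Two other statements bear on the number of pairs. The Study Protocol section says "We conducted a 6-week intervention among 50 dyads". The Statistical Analysis Plan section names the test and the handling of missing data: "An intent-to-treat analysis using one fully-imputed dataset and paired t-tests were used". No pre-post correlation, number of completers or enrolment figure above 50 appears anywhere.

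**The concern.** The power sentence contains every input needed to check it, and it says that attrition has been allowed for. Read directly, 50 dyads less 10% is 45 pairs, and the stated power does not follow at 45. The figure looks like one worked out for nearly the full 50 and then described as if attrition had been taken off.

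The first goal in the Statistical Analysis Plan is to establish whether pre-post changes are statistically significant, so the stated sensitivity affects how a null result is read. At d = .41 the chance of missing a real change is about 23%, where the plan implies less than 20%. No decision rule is tied to power, so the consequence stops at the accuracy of the statement.

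**Working it through.** **Inputs, all from the document.** 50 dyads, 10% attrition, two-sided alpha .05, d = .41 and power > .80 come from the Power Analysis; the paired t-test comes from the Statistical Analysis Plan. The d is taken as the mean change divided by the SD of change, because the plan gives it as an effect size for change. Each student or parent contributes one pre-post pair, so the number of pairs equals the number of dyads.

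**Formula.** Power = P(|T| > t_crit), where T is noncentral t with n − 1 degrees of freedom and noncentrality d√n.

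**Looking for the plan's figure.** With no attrition, n = 50: noncentrality .41 × √50 = 2.899, t_crit (49 df) = 2.010, power **.811**. This agrees with > .80.

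**Applying the stated attrition.** 50 × .90 = 45: noncentrality .41 × √45 = 2.750, t_crit (44 df) = 2.015, power **.767**.

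| Analysed pairs | Power at d = .41 | d detectable at .80 power |
|---|---|---|
| 45 | .767 | .427 |
| 46 | .777 | .422 |
| 47 | .786 | .417 |
| 48 | .794 | .413 |
| 49 | .803 | .408 |
| 50 | .811 | .404 |

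Power first exceeds .80 at 49 pairs: one dyad lost of 50, or 2%.

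**Could a small technical choice explain the gap?**
- Rounding of d: at 45 pairs d = .415 gives .777.
- Normal approximation at 45 pairs: Φ(2.750 − 1.960) = .785, still below .80.
- One-sided .05 at 45 pairs: .856, but the plan says two-tailed.

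**Does the imputed dataset restore the power?** It keeps 50 rows in the test, so this was simulated: 60,000 trials per setting, 5 of 50 posttests missing completely at random, regression imputation from the pretest, and a paired t-test on all 50 rows. The pre-post correlation is not given, so .5 and .7 were assumed.

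| Correlation | Imputation | Nominal power | Type I error | Power at a true .05 |
|---|---|---|---|---|
| .5 | stochastic | .795 | .067 | .756 |
| .5 | deterministic | .823 | .071 | .780 |
| .7 | stochastic | .790 | .070 | .744 |
| .7 | deterministic | .825 | .073 | .772 |

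Where nominal power passes .80, the test is rejecting too often under the null. Held to the plan's alpha, power is .74 to .78.

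**Correlations.** If .80 power and two-sided .05 are meant, power for r = .38 depends on the method:

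| n | Fisher z | Exact bivariate normal | Fixed predictor |
|---|---|---|---|
| 45 | .737 | .746 | .769 |
| 50 | .783 | .791 | .812 |

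The r detectable at .80 power with n = 45 is .407, .403 and .393 respectively. So r = .38 is unsupported at 45. It is marginal even at 50, and so does not itself show that attrition was left out.

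**The case against.** The strongest reply is that 50 may already be the number left after attrition. Power is then .811 and the sentence is correct. That reading is possible, but it implies 50/.9 = 55.6, so about 56 dyads enrolled. The document states no number above 50 and reports the intervention in 50 dyads. Even on this reading the text needs a clarification.

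A second reply is that the plan does not say which SD standardises d. If it is the raw-score SD, with equal SDs at both times, the standardised change is .41/√(2(1 − ρ)). At 45 pairs power is then .767 at ρ = .5, .853 at ρ = .6 and .935 at ρ = .7; it passes .80 once ρ is about .54 or more. Such correlations are plausible, so the .767 is conditional on d being the standardised change. That is the natural reading of an effect size given for change, and the rescue needs a correlation that the plan does not supply.

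A third reply is that the imputed analysis has 50 rows and its nominal power straddles .80. That is true, but a single imputed dataset adds no information about the lost pairs. The simulation does rest on assumptions outside the document (pretest-only imputation, missingness completely at random, the assumed correlations), so it serves only to answer this reply; the main finding does not need it.

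Finally, the gap is small, and the document describes a completed feasibility study in the past tense, so correcting it cannot improve planning. That is fair, and it limits the weight of the point. It does not make the sentence right.

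**Conclusion.** The concern holds. From the plan's own inputs, power at d = .41 is about .77, roughly 3 points below the stated bound, and the effect detectable at .80 power is about d = .43. This rests on two readings of the text: that 50 is the number before attrition, and that d is standardised by the SD of change. Both are the direct readings, and each alternative needs a figure that the document does not give. The r = .38 sentence is a lesser point, since it states neither power nor alpha. Conduct and enrolment are unaffected. It should be fixed because the statement is wrong as written and the correction is nearly free.

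**What to change.** Restate the Power Analysis in one of three ways:

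- **Restate the effect.** *With 50 dyads and 10% attrition (45 analysable pairs), two-tailed alpha .05, power is .80 to detect d of about .43 for change and r of about .40 for ancillary correlations.*
- **Restate the power.** Keep d = .41 and r = .38, and give power of about .77 and .75 at 45 pairs.
- **Clarify the number.** If 50 was meant as the number after attrition, say so and give the number enrolled (about 56 at 10% loss). The d = .41 then stands at power .81.

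In each case attach a power and an alpha to the correlation sentence, and say that d is standardised by the SD of change.

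The cost is one or two sentences and slightly less favourable stated figures. Design, enrolment and analysis do not change.
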